9.2 Rationale for Study Design and Study Drug Regimens

9.2.1 Study Design

The study is designed to evaluate early response to VX-509 administration, including local synovial and bone response assessment by MRI imaging and synovial biopsy (Section 6.5). The double-blind placebo-controlled design will allow comparison to variability in efficacy parameters for control subjects. No blinded joint assessor is utilized in the trial due to the small subject numbers and partial unblinding of all arthroscopy subjects, who are randomized to the 200 mg qd dose of VX-509 (Arm C) to avoid the variability inherent with doseranging. Due to the increased assay sensitivity of joint MRI, and blinded reading by 2 central readers, there is improved study power to detect RAMRIS differences and the validity of MRI data is maintained. As a sensitivity analysis, the ACR20-CRP and DAS28-4(CRP) efficacy parameters will be re-evaluated without inclusion of the arthroscopy subjects.

9.2.2 Study Drug Dose and Duration

VX-509 doses between 100 mg qd and 200 mg qd are currently being evaluated in Study VX11-509-102 (Study 102), a Phase 2b study for RA subjects receiving background MTX. In Phase 2a Study 101, total daily doses of 100, 200, and 300 mg were shown to be safe and efficacious when administered using twice per day (bid) regimen (50, 100, or 150 mg bid). This study is the first clinical study conducted with VX-509 in subjects with RA to evaluate concurrent treatment with VX-509 300 mg qd and a DMARD for 12 weeks.

9.2.3 Rationale for Dosing Regimen

In Study VX10-509-004 (Study 004), VX-509 doses of 150 mg every 12 hours (q12h) and 300 mg qd were administered to healthy subjects in a crossover design.³⁷ The results indicated that the qd and bid dosing regimens resulted in a similar total daily exposure (AUC from the time of dosing to 24 hours [AUC₀₋₂₄]) to VX-509 (Table 9-1).

Table 9-1 Total Daily Exposure to VX-509 in Study VX10-509-004

	AUC _{0-24h} (hr•μg/mL)		
Dose Regimen	Mean (SD)	$C_{max} (\mu g/mL)$	C_{min} ($\mu g/mL$)
150 mg q12h	24.0 (5.15) ^a	1.95	0.349
300 mg qd	24.0 (5.32)	3.67	0.109

Source: Study VX10-509-004.³⁷

 AUC_{0-24h} : area under the concentration versus time curve from the time of dosing to 24 hours; bid: twice per day; C_{max} : maximum observed plasma concentration; C_{min} : minimum observed plasma concentration; q12h: every 12 hours; qd: once daily.

Based on a review of clinical studies involving other JAK3 inhibitors with a mechanism of action similar to that of VX-509, using a simulation from the PK profile of CP-690,550 (JAK1/JAK3 inhibitor), it is apparent that clinical improvement in RA only requires intermittent inhibition of JAK3 greater than 50% (concentration resulting in 50% of maximum inhibition [IC $_{50}$] of approximately 24 ng/mL) for about 4 to 6 hours in every 12 hour period. ^{38,39,40} The VX-509 dosing levels of 100 mg qd and above yield

^a Value is $2 \times AUC_{0-12h}$ for 150 mg q12h.

approximately 6 hours of >50% inhibition (VX10-509-004; simulated data not shown). Considering VX-509 has a moderate half-life of approximately 8 hours, once daily dosing is feasible and was selected for this study.

9.2.4 Safety Margin

Estimated daily exposure based on doses from Study 004^{37} (healthy subjects) and Study 101^{31} (RA subjects) is summarized in Table 9-2. Using these projections, the estimated safety margin at the clinical dose of 300 mg/day based on exposures observed at the no observable adverse effect level (NOAEL) in rats and dogs during chronic toxicity studies is approximately 2.7- and 3.5-fold, respectively (Table 9-3).

Table 9-2 Estimated Daily Exposure to VX-509 in Study VX12-509-103, from Study VX10-509-004 and Study VX09-509-101 Data

Dose	AUC _{0-24h} (μg•hr/mL)	C _{max} (µg/mL)	C _{min} (µg/mL)
100 mg qd	9.46 ^a	1.22 ^b	0.036^{b}
200 mg qd	19.9 ^a	2.45 ^b	0.073^{b}
300 mg qd	33.4^{a}	3.67^{c}	0.109^{c}
100 mg bid	19.9 ^a	1.21 ^d	0.477^{d}

Sources: Study VX-509-101;^{31,41} Study VX10-509-004.³⁷

 AUC_{0-24h} : area under the concentration versus time curve from the time of dosing to 24 hours; bid: twice per day; C_{max} : maximum observed plasma concentration; C_{min} : minimum observed plasma concentration; qd: once daily.

Values obtained by $2 \times AUC_{0-12h}$ of corresponding daily equivalent bid dose (e.g., 50 mg bid for 100 mg qd) for RA subjects in Study 101. 31,41

Values obtained by applying fraction of dose (one third; two third) to the observed 300 mg qd value from healthy subjects in Study 004.³⁷

Observed value from healthy subjects in Study 004.³⁷

d Observed value from RA subjects in Study 101.³¹

Observations at NOAEL	Observed (Rat/Dog) AUC _{0-24h} (μg•hr/mL)	Estimated AUC _{0-24h} (µg•hr/mL) at Clinical Dose of 300 mg qd ^a	Estimated Safety Margin at Clinical Dose of 300 mg qd
Male rats	89.5	33.4	2.68
Female rats (NOAEL based on uterine atrophy finding)	7.83	33.4	0.23 (2.68) ^b
Male dogs	102	33.4	3.05
Female dogs	117	33.4	3.50

Table 9-3 Estimated Chronic Non-Clinical Safety Margin over Estimated Clinical Exposure at VX-509 Dose of 300 mg/day

Sources: VX-509 Investigator's Brochure³⁶, Study VX-509-101;^{31,42}

 AUC_{0-24h} : area under the concentration versus time curve from the time of dosing to 24 hours; C_{max} : maximum observed plasma concentration; NOAEL: no observable adverse effect level; qd: once daily.

9.2.5 Previous Clinical Findings

In 3 Phase 1 studies, VX-509 was administered as single doses from 10 to 900 mg, and as multiple daily doses of 25 to 600 mg for 7 or 14 days (Study VX08-509-001, Study VX08-509-002, and Study VX10-509-004). Overall, the results demonstrated that VX-509 was safe and well-tolerated with administration of multiple doses of up to 600 mg daily for 14 days in normal healthy volunteers. One subject receiving a single 900 mg dose of VX-509 developed symptoms of nausea, vomiting, headache, and tremor. This subject was found to have a higher plasma VX-509 exposure (173 μg•hr/mL), which exceeded the exposure level at the NOAEL in all nonclinical species.

Data from a 12-week Phase 2a study (Study 101) of VX-509 administration in 204 RA subjects demonstrated that ACR20-CRP responses at Week 12 were achieved in 29%, 39%, 61%, 65% and 66% of the placebo, 25-, 50-, 100- and 150-mg bid VX-509 groups, respectively ($P \le 0.007$ for the 3 highest doses). Statistically significant improvement was also seen for the 3 highest doses in DAS28-4(CRP) at Week 12 (P < 0.001).

The most frequent adverse events (AEs) were infections, seen in approximately 17% of both placebo and VX-509 subjects, although more frequently in higher VX-509 dose groups. There were 11 treatment-emergent serious adverse events (SAEs) seen in 9 subjects (10 SAEs in 8 VX-509 subjects) and SAEs were more frequent in the higher VX-509 dose groups. There were 5 SAEs in the infections and infestations system organ class, all in subjects receiving VX-509, including bronchitis, erysipelas, pneumonia, tuberculosis, and osteomyelitis. There were 2 fatal SAEs of subarachnoid hemorrhage and pneumonia in VX-509 subjects.

Primarily Grade 1 increases ALT or AST values, and increases in both low density lipoprotein (LDL)- and high density lipoprotein (HDL)-cholesterol were observed in subjects who received higher doses of VX-509. For further information refer to the VX-509 Investigator's Brochure.³⁵

^a In Study VX09-509-101, estimated AUC_{0-24h} for 300 mg qd was 33.4 μg•hr/mL (Table 9-2).

Uterine and mammary gland atrophy are considered to be rat species-specific findings.³⁶ Based on the male rat NOAEL (60 mg/kg/day), the safety margin for female rats would also be 2.68.

9.2.6 Drug-Drug Interaction Potential with Required DMARDs and Corticosteroids

Drug-drug interaction studies of VX-509 with the DMARDs required in the current study have not been conducted. In Study 102, the potential interactions of VX-509 and MTX will be explored, but these data are not yet available.

VX-509 is mainly metabolized in the liver through oxidation by cytochrome P450 34A CYP3A4, and subsequent glucuronidation, sulfate conjugation, and hydrolysis. Only approximately 1% of VX-509 is renally excreted unchanged in urine in humans. The protein binding of VX-509 is approximately 81% to 91%. ³⁶

VX-509 may slightly increase the level of corticosteroid exposure in subjects, therefore close monitoring of steroid side effects is recommended. If necessary, adjustments should be made as detailed in Section 10.3.

For MTX, 80% to 90% of MTX is excreted unchanged renally. Therefore, drug-drug interaction between VX-509 and MTX are unlikely as VX-509 is not expected to interfere with the renal clearance of MTX.

For leflunomide, its definitive metabolic pathway has not been established. Most likely, leflunomide is metabolized via CYP1A2. 45,46 The active metabolite of leflunomide, M1, is most likely metabolized through CYP2A6. Therefore, drug-drug interaction between VX-509 and leflunomide is unlikely as VX-509 is not expected to interfere with CYP1A2 and CYP2A6 on which leflunomide and M1 metabolism depend.

Penicillamine, a chelating agent, appears in the plasma as free penicillamine, penicillamine disulfide, and cysteine-penicillamine disulfide, and is mainly excreted renally as disulfide. It may interact with food, antacids, and iron, which may interfere with the formation of chelating compounds, and is therefore best dosed while fasting. Drug-drug interaction of VX-509 and penicillamine coadministration is unlikely, if VX-509 and penicillamine are not taken simulataneously.

Sulfasalazine, a probiotic agent, is absorbed quickly and almost completely. ⁴⁹ Sulfasalazine is metabolized via intestinal bacteria to its active metabolites, sulfapyridine (SP) and 5-aminosalicylic acid (5-ASA). Absorbed SP and 5-ASA and their metabolites are primarily eliminated in the urine either as free metabolites or as glucouronide conjugates. Drug-drug interaction of VX-509 and sulfasalazine coadministration is unlikely.

9.2.7 Other Considerations

VX-509 was shown to be teratogenic in rat and rabbit embryo-fetal studies in doses equal to or above human equivalent doses which will be investigated in the current study (the VX-509 Investigator's Brochure provides specific details about the nonclinical findings).³⁶ The effect of VX-509 on oral contraceptives has not been studied. Subjects will be required to use appropriate contraception as detailed in Section 12.9.6.1.

9.2.8 Overall Risk Benefit Estimation

Taking the risk/benefit factors together, these results support the selection of the doses used in this study (placebo, 100 mg, 200 mg, and 300 mg VX-509 qd). The doses are anticipated to be within the therapeutic window and will have adequate safety margins.

9.2.9 Rationale for Study Assessments

The study assessments for the primary and secondary endpoints (i.e., ACR, DAS, and EULAR) for this protocol are validated and accepted for use in clinical studies in RA to assess efficacy.

MRI of an inflamed joint is a sensitive measure of change, and MRI at Week 4 has shown significant improvement in bone marrow edema (osteitis) with TNF inhibition, as compared to placebo plus background DMARD.²² MRI evaluations at Weeks 6 and 12 will be utilized to evaluate early change in synovitis and osteitis, a predictor of therapeutic inhibition of radiographic structural damage.

10 SELECTION OF STUDY POPULATION

Subject eligibility should be reviewed and documented by an appropriately qualified member of the investigator's study team before subjects are included in the study.

10.1 Inclusion Criteria

Subjects who meet all of the following inclusion criteria will be eligible for this study:

- 1. Must sign and date an informed consent document.
- 2. Male and female subjects between the ages of 18 and 65 years, inclusive, on the day the informed consent is signed.
- 3. Diagnosed with RA as defined by the 1987 ACR revised criteria and RA duration at screening of at least 24 weeks.
- 4. Seropositivity based on either a positive rheumatoid factor or anti-cyclic citrullinated peptide (anti-CCP) antibody at screening **OR** known erosive disease based on previous X-ray report (available and filed) or erosions detected on baseline hand and foot X-ray.
- 5. Subjects must have palpable 2+ synovitis of the wrist or ≥2 MCPs, defined as loss of bony contours with palpable joint effusion and/or swelling, in the MRI-designated hand (the hand being used in MRI assessments).
- 6. Subjects must be receiving stable therapy with 1 of the following DMARDs: methotrexate, sulfasalazine, leflunomide, anti-malarial drug, or penicillamine. Stable therapy with 1 anti-malarial drug may be continued alone or with 1 of the other DMARDs listed above. Stable therapy is defined as initiation of the DMARD at least 16 weeks before screening and no change for the 8 weeks immediately before screening. The DMARD dose must remain the same throughout the study. Any increase, decrease, or change in the DMARD dose is prohibited during a subject's participation in the study,

- except for a dose reduction that is mandated for toxicity. The required dose ranges for each of these DMARDS are summarized in Section 10.3.
- 7. Subject must have a swollen joint count of ≥ 6 out of 66 assessed joints and a tender joint count of ≥ 8 out of 68 assessed joints at screening and Day 1. Joints in which there has been a total joint replacement will be excluded from the joint counts.
- 8. Baseline CRP level \geq 1.2 × ULN or Westergren erythrocyte sedimentation rate \geq 1.2 × ULN at screening.
- 9. Subjects in the synovial biopsy subset must additionally have palpable 2+ synovitis, defined as loss of bony contours with palpable joint effusion and/or swelling, of the knee or the wrist in the non-MRI-designated hand (the wrist not being used in MRI assessments) to be biopsied; this joint must not have received a total joint replacement.
- 10. Subject must be willing and able to comply with scheduled visits, treatment plan, lifestyle guidelines, concomitant medication guidelines, laboratory tests, vaccination rules, contraceptive guidelines, and other study procedures.

10.2 Exclusion Criteria

Subjects who meet any of the following exclusion criteria will **not** be eligible for this study:

- 1. Inflammatory and rheumatological disorders other than RA, where arthritis may be a prominent feature, such as systemic lupus erythematosus, mixed connective tissue disease, scleroderma, poly/dermatomyositis, or gout; secondary Sjogren's syndrome or interstitial lung disease are allowed.
- 2. History of any illness that might confound the results of the study or pose an additional risk in administering study drug(s) to the subject. This may include, but is not limited to, history of cardiovascular or central nervous system disease, history or presence of clinically significant abnormalities on physical exam, ECG or laboratory examination, or history of clinically significant psychiatric or mental disease.
- 3. History of cancer, except squamous or basal cell cancers of the skin or in situ cancer of the cervix.
- 4. History of hematologic disorders including neutropenia and thrombocytopenia other than Felty's syndrome.
- 5. History of tuberculosis (TB), regardless of history of anti-mycobacterial treatment; or active TB as determined by X-ray, TB skin test and QuantiFeron® TB Gold Assay (QuantiFeron assay). If the subject has a hypersensitivity to skin test preparation associated with the TB skin test then the QuantiFeron alone is acceptable.
- 6. Acute or chronic active infection requiring systemic antimicrobial treatment with the exception of onychomycosis receiving antifungal medication, or acne and rosacea receiving low-dose antibiotics.
- 7. History of febrile illness within 5 days before the first dose of study drug.
- 8. History of previous osteomyelitis, infected joint or joint prosthesis.

- 9. Subjects who are at high risk of developing an infection due to a compromised immune system including poorly controlled diabetes.
- 10. Weight <45 kg at screening.
- 11. A 12-lead ECG demonstrating QT interval corrected (QTc) >450 msec at the screening Visit. If QTc exceeds 450 msec, the ECG should be repeated 2 more times, and the average of the 3 QTc values used to determine the subject's eligibility. Subjects should also be excluded if any other clinically significant interval (e.g., PR prolongation), morphologic (e.g., T-wave inversion), or conduction abnormalities are observed.
- 12. Planned surgery during the study.
- 13. Metal implant or other contra-indication to MRI scanning.
- 14. History of alcohol or drug abuse, or excessive alcohol consumption as determined by the investigator, during the previous 12 months before screening.
- 15. For female subjects: Pregnant or nursing; or planning to become pregnant during the study or within 90 days following the last VX-509 dose; or female subjects of childbearing potential who are unwilling or unable to use an acceptable method of contraception as outlined in this protocol from at least 14 days before the first dose of study drug and for 90 days following the last dose of study drug.
- 16. For male subjects: Subject has a female partner who is pregnant, nursing, or planning to become pregnant during the study or within 90 days following the last VX-509 dose; or male subjects who are unwilling or unable to use an acceptable method of contraception as outlined in this protocol from at least 14 days before the first dose of study drug and for 90 days following the last dose of study drug.
- 17. Subject is the investigator or a subinvestigator, research assistant, pharmacist, study coordinator, other staff, or a relative of study personnel directly involved with the conduct of the study.
- 18. Requirement for more than 1 NSAID after signing informed consent at screening (additional aspirin [second NSAID] ≤325 mg/day is allowed). The dose of any ongoing NSAID must be stable for at least 28 days before Day 1.
- 19. Systemic corticosteroid treatment (prednisone or equivalent) >10 mg/day. The dose of any ongoing systemic corticosteroid must be stable for at least 28 days before Day 1 (Section 16.13).
- 20. Allergy to gadolinium.
- 21. Prior treatment with a JAK inhibitor.
- 22. Other DMARDs (biologic/non-biologic) beyond the required DMARD for study entry must have been discontinued for specified minimum periods before screening (see Section 16.2). Subjects with prior treatment with rituximab/ocrelizumab (or other depleting monoclonal antibody) must show demonstrated recovery of any cytopenia(s).
- 23. Intraarticular corticosteroids in any joint within 4 weeks before screening, or within 12 weeks before screening for the MRI-designated hand or joint planned for arthroscopy.

- 24. Treatment with an investigational drug within 60 days or 5 half-lives preceding the first dose of study drug, whichever is longer.
- 25. Subjects who require concomitant use of any moderate or strong inhibitors or inducers of CYP3A or P-gp or who require CYP3A substrates with serious associated side effects at high exposure (Section 10.3; partial lists in Section 16.3).
- 26. Have received a live or live attenuated vaccination in the 4 weeks before study Day 1.
- 27. Positive urine or serum pregnancy test.
- 28. Hemoglobin <11 g/dL for females or <12 g/dL for males at screening.
- 29. Absolute neutrophil count <1.5 K/μL at screening.
- 30. Platelet count <120 K/μL at screening.
- 31. ALT or AST \geq 1.5 × the ULN at screening.
- 32. Creatinine clearance <30 mL/min at screening
- 33. Positive hepatitis B surface antigen, hepatitis C virus antibody, or human immunodeficiency virus 1 and 2 antibodies at screening.
- 34. Other clinically significant out-of-range laboratory results in hematology, serum chemistry, coagulation studies, or urinalysis at the screening as judged by the investigator.

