Adjusted instructions about the joint numbers that need to be assessed during Magnetic Resonance Imaging (MRI); specified that at a minimum the wrist and the metacarpophalangeal [MCP] joints #2 to #5 must be assessed. This adjustment was made based on functional feasibility at the site. Further details will be provided in the Imaging Guideline.	Sections 2, 8.1, and 12.8.1
The following endpoints were added:	Sections 2, 8.2, and 8.3
 Secondary: Change from baseline in Health Assessment Questionnaire –Disability Index (HAQ-DI) at Week 12. Other: Change from baseline in OMERACT RAMRIS joint space narrowing score at Weeks 6 and 12 	
These endpoints were left out in error as their analysis was already described in the protocol.	
Clarified when the baseline X-ray of hands and feet will be performed.	Sections 2, 3, and 10.1 (inclusion #4)
Clarified eligibility requirements related to the tuberculosis (TB) test to indicate that subjects will not be eligible if they have a history of TB, regardless of history of antimycobacterial treatment; or active TB as determined by X-ray, TB skin test and QuantiFeron [®] TB Gold Assay (QuantiFeron assay). Guidance was also added to indicate that if the subject has a hypersensitivity to skin test preparation associated with the TB skin test then the QuantiFeron alone is acceptable.	Section 10.2 (exclusion #5)

Change and Rationale	Affected Sections
Language specifying that the DMARD dose must remain the same throughout the study was clarified to allow investigators to make dose adjustments as necessary for safety and toxicity.	Sections 2 and 10.3
ECG assessment language was previously updated to indicate that ECG vendor service will provide the ECG machines to sites that need them for use during the study. This is no longer the case. ECG assessment language has also been revised to match current standards at Vertex.	Section 12.9.5
Details related to the type of scanner to be used for conducting MRI were removed. Further details will be provided in the Imaging Guideline.	Sections 2 and 12.8.1
Contraceptive requirements have been revised to match updated requirements for the VX-509 development program.	Sections 12.9.6 and 12.9.6.2

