12.9.2 Clinical Laboratory Assessments

Blood and urine samples for the procedures described in Table 12-1 will be analyzed at a local or central laboratory. Subjects must abstain from all food and drink (except water) at least 8 hours before blood draws for the fasting lipid profile. Laboratory test results that are abnormal and considered by the investigator to be clinically significant must be reported as adverse events.

Table 12-1 Safety Laboratory Test Panels

Serum Chemistry	Hematology	Urinalysis
Glucose	Hemoglobin	Leukocytes
Blood urea nitrogen	Red blood cell count	Nitrite
Creatinine	Mean corpuscular hemoglobin	Urobilinogen
Creatine kinase	Mean corpuscular hemoglobin concentration	Protein
Sodium	Mean corpuscular volume	рН
Potassium	Platelet count	Blood
Calcium	Reticulocyte count	Specific gravity
Chloride	White blood cell count	Ketones
Magnesium	Differential (absolute and percent):	Bilirubin
Inorganic phosphate	Eosinophils	Glucose
Total and indirect bilirubin	Basophils	
Alkaline phosphatase	Neutrophils	Microscopy: *
Aspartate transaminase	Lymphocytes	Casts
Alanine transaminase	Monocytes	Bacteria
Lactate dehydrogenase		Red blood cells
Total protein		White blood cells
Albumin		
Uric acid		* If gross urinalysis is positive
Iron Studies (baseline only)		for leukocytes, erythrocytes,
Serum iron		nitrite, protein, or bilirubin, microscopic examination of
Ferritin		urine will be performed.
Total iron-binding capacity		will be performed.

Additional Evaluations

Coagulation studies: Activated partial thromboplastin time; prothrombin time; and International Normalized Ratio.

Inflammation tests: C-reactive protein, and Westergren erythrocyte sedimentation rate

Fasting lipid profile: Total Cholesterol, HDL-C, LDL-C, LDL-C/HDL-C ratio, triglycerides. Leptin and lipoprotein (a) will be assessed as part of this profile only on Day 1 and at the Week 12/Early Discontinuation Visit.

Erythropoietin

Serology: Hepatitis B surface antigen, hepatitis C virus antibody, human immunodeficiency virus 1 antibody, and human immunodeficiency virus 2 antibody.

Tuberculin skin testing: A 5 tu purified protein derivative (PPD) skin test will be positive if >10 mm at 48 to 72 hours.

QuantiFeron® **TB Gold Assay**: Serum incubation and enzyme-linked immunosorbent assay (ELISA) testing for latent tuberculosis.

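### Exclusion 5 bars a history of TB or active TB, so a subject with a clear chest X-ray and a positive skin test or QuantiFERON meets no specific exclusion

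*Protocol*

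**What the plan says.** Exclusion 5 in Protocol Section 10.2 has two limbs.

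- The first is strict: "History of tuberculosis (TB), regardless of history of anti-mycobacterial treatment".
- The second is "or active TB as determined by X-ray, TB skin test and" QuantiFERON.

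One further sentence deals with subjects who are hypersensitive to the skin-test preparation: "then the QuantiFeron alone is acceptable".

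The Summary of Changes, which agrees with the current text here, presents the criterion as a rule about testing: "Clarified eligibility requirements related to the tuberculosis (TB) test to indicate that subjects will not be eligible if they have a history of TB". It underlines the conjunction in "TB skin test and QuantiFeron".

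Both immunological tests are scheduled for every subject at screening (Table 3-1; Section 13.3.2.4). Table 12-1 in Section 12.9.2 gives the purpose of the QuantiFERON assay as "testing for latent tuberculosis". A positive skin test is defined twice: at least 10 mm in the footnote to Table 3-1, and more than 10 mm in Table 12-1. Section 13.3.2.4 sends the results of both tests to data listings.

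**The concern.** The second limb names active TB as the condition that excludes, yet one of the tests it relies on is described elsewhere in the protocol as a test for latent infection. The criterion never says that a positive result is itself a reason for exclusion. A positive immunological test with a normal chest X-ray is the case that a latent-infection assay exists to find, and it is the case for which the protocol sets no rule.

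The stake is patient safety. The study adds a JAK3 inhibitor to a background DMARD. Section 9.2.2 says this is the first study in RA subjects of 300 mg once daily with a DMARD for 12 weeks. Section 9.2.5 lists tuberculosis among the infection SAEs of the Phase 2a study, all of which occurred on VX-509. With no explicit rule, one site may enrol a test-positive subject whom another would refuse, and both could point to the protocol.

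**Working it through.** There is no figure to reproduce. The check takes one hypothetical subject through every provision that might apply: no TB history, a clear chest X-ray, and a positive skin test, a positive QuantiFERON, or both.

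**Exclusion 5, history limb.** Not met, by construction.

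**Exclusion 5, test limb.** The trigger is active TB. Take the reading most favourable to the protocol: all three investigations are done and the investigator then decides. The X-ray is clear, and by the protocol's own description a positive QuantiFERON points to latent infection. Active TB is not shown, so the limb is not met.

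**Other exclusions in Section 10.2.**

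- Exclusion 6 requires an active infection needing systemic antimicrobial treatment. A positive test alone does not establish that.
- Exclusion 9 concerns infection risk from a compromised immune system. A positive TB test is not such a condition.
- Exclusion 33 is triggered by positive results, but only for hepatitis B, hepatitis C and HIV.
- Exclusion 34 covers significant out-of-range results in four groups: hematology, serum chemistry, coagulation and urinalysis. The TB tests belong to none of them.
- Exclusion 2 can apply. It reaches illness that might "pose an additional risk in administering study drug(s) to the subject" and includes "history or presence of clinically significant abnormalities on physical exam, ECG or laboratory examination". QuantiFERON sits in the safety laboratory table, so it can count as a laboratory examination. The clause still requires someone to judge the result clinically significant or the risk material.

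**Remaining provisions.** The footnote to Table 3-1 and Table 12-1 define a positive skin test but attach no eligibility consequence to it. Section 13.3.2.4 only lists the results. No section sets a rule for latent TB or requires preventive treatment.

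**Result.** No specific exclusion applies. One general clause may apply, at the investigator's discretion.

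**Cut-off.** An induration of exactly 10 mm is positive under the Table 3-1 footnote (10 ≥ 10) and negative under Table 12-1 (10 is not > 10). Any rule that relies on a positive skin test has to settle this.

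**The case against.** A reader might infer that the conjunction requires all three results to be positive before anyone is excluded. The protocol does not support that as the meaning. The hypersensitivity sentence is about which tests must be done. Section 13.3.2.4 likewise speaks of both tests being conducted. Exclusion 33 joins HIV 1 and HIV 2 with the same word although either result is plainly meant. The underlining in the Summary of Changes fits an instruction to perform both tests at least as well. The point therefore does not rest on that reading.

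The opposite inference is also tempting: that any positive result was always meant to exclude. The strict history limb and the way the Summary of Changes frames the rule make this plausible. The criterion does not say so, however, and the word active points the other way.

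The strongest defence is that exclusion 2 already covers the case, that many criteria depend on clinical judgement, and that Section 10 requires a qualified team member to review and document eligibility. This is partly right: the subject is not beyond the reach of the exclusions. What remains is that an important safety decision rests on a general clause that does not mention TB, while the criterion written for TB leaves the case out.

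It can also be said that describing QuantiFERON as a latent-TB test merely describes the assay, and that using it in a TB work-up is no contradiction. That is fair. The weakness is the missing consequence of a positive result, not the choice of test.

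**Conclusion.** The gap is real and should be fixed. As worded, exclusion 5 does not cover a test-positive subject with a clear chest X-ray and no TB history. Such a subject is barred only if the investigator invokes exclusion 2. This holds under the mild reading, in which all tests are performed and the investigator decides whether TB is active.

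The size cannot be given as a number of patients. The protocol states no expected rate of positive skin tests or QuantiFERON results, so neither the number admitted nor the number of inconsistent decisions can be estimated.

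A reader might take the Phase 2a tuberculosis SAE as evidence that latent infection was reactivated after similar screening. The protocol says neither whether it was reactivation nor how that study screened. The event shows that the topic matters for this drug and nothing more.

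Confidence is moderate, because the sponsor may have intended any positive result to exclude. If so, the rewording only puts that intent on paper.

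**What to change.** Reword exclusion 5 along these lines:

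*History of TB, regardless of anti-mycobacterial treatment; or chest X-ray suggestive of TB; or a positive TB skin test (≥10 mm induration at 48 to 72 hours) or a positive QuantiFERON assay at screening. Both tests must be performed, except that QuantiFERON alone suffices in a subject hypersensitive to the skin-test preparation.*

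Change the cut-off in Table 12-1 from more than 10 mm to at least 10 mm, so that it matches the footnote to Table 3-1.

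The cost is one amended criterion and one corrected table entry. No test is added: the skin test and QuantiFERON are already scheduled at screening, the chest X-ray is taken then or available from the preceding 12 weeks, and QuantiFERON is already recorded as positive or negative. The downside is some additional screen failures, including false positives, in a number that the protocol does not allow to be estimated.
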